2.1.2 Clinical Trial Rationale

Selectively neutralizing sTNF will have several benefits. sTNF is the cytokine that both promotes transmigration of leukocytes from the blood vessel to the lung parenchyma and stimulates the cytokine secretion of leukocytes in the tissue that causes cell damage and edema resulting in hypoxia. Neutralization of sTNF will prevent leukocyte infiltration of pulmonary tissue and decrease inflammation of cells already in the extracellular compartment. Because of the need to stop the CS, early treatment is ideal to both prevent progression of pulmonary pathology to ARDS as long as the therapy does not compromise the immune response to the virus (Shi *et al.* 2020).

INB03 is a recombinant protein variant of the soluble form of native human TNF that has mutations engineered in the TNFR binding interfaces that eliminate its ability to bind to or activate TNFR1 and TNFR2. INB03 is a first-in-class agent that acts by a novel dominant-negative mechanism to eliminate pro-inflammatory sTNF homotrimers through exchange of monomeric subunits between the compound and the native cytokine. INB03 does not activate TNF-associated signalling pathways, acting only by exchanging subunits with sTNF, thereby destroying the biological activity of sTNF.

INB03 is not immunosuppressive. It has shown to reduce inflammation in multiple infectious disease models without compromising the immune response to infection or affecting mortality (Zalevsky *et al.* 2007, Olleros *et al.* 2009, 2010, Maillet *et al.* 2011, Vanwalleghem *et al.* 2017, Liu *et al.* 2019). INB03 can be given prophylactically to prevent disease progression without a negative effect on the ability of the immune system to fight the infection – viral and bacterial. These characteristics may even improve the ability of the patient to recover from ARDS.

Because the drug targets an important inflammatory cytokine that drives the development of pulmonary complications of COVID-19, is not immunosuppressive acutely (it does not worsen the immune response to bacterial or viral infection), is safe and well tolerated at the proposed dose and is simple to administer (up to 2 subcutaneous doses over a 8 day period), the proposed trial will target older patients who have a diagnosed COVID-19 infection with pulmonary complications. This is a high-risk group of patients that can deteriorate rapidly requiring

CONFIDENTIAL

intensive care beds and increased respiratory support. INB03 is not an anti-viral therapy. Therapy is not expected to decrease viral load, ability of the participant to infect others or length of active infection or shedding. The goal of the study is to prevent symptomatic participants from getting worse. If INB03 can safely prevent progression of COVID-19 related symptoms so that participants do not end up requiring intensive care and ventilatory support, this should decrease mortality and decrease the intense resource pressures on the health care system.

The trial focuses on high risk adult patients. Many of these patients will have at least one co-morbidity (obesity, hypertension, cardiovascular disease, diabetes, Black/African-American race or Hispanic/Latino ethnicity). This population is most likely to develop complications of COVID-19 infection requiring admission to ICU including respiratory embarrassment. Younger patients do develop symptomatic disease, but they rarely progress to the point of requiring ventilatory support. Follow-up has been streamlined because much of the medical system is focused on inpatient care. Every attempt has been made to allow that focus to continue. As such, the trial is designed to simplify care of the patients during the surge of COVID-19 infections and hospital admissions.

In addition to the acute complications of COVID-19, a subset of patients will have persistent symptoms and become “long-haulers” (Rubin 2020, Greenhalgh et al. 2020). Although this is an emerging population with no strict definitions, these patients experience symptoms lasting beyond three weeks after recovery from acute COVID-19 (Greenhalgh et al. 2020). The emerging data on Long COVID patients suggests a high prevalence of symptoms such as dysautonomia, fatigue, cognitive, and mood, among others (Davis et al. 2020).

These core symptoms of Long COVID such as cognitive dysfunction, fatigue, and depression mirror sickness behaviors which are induced by pro-inflammatory cytokines, specifically TNF (Kelly and Kent 2020). To this end, COVID-19 triggers long-lasting changes in the immune system (Rubin 2020), suggesting that long-COVID symptoms are a consequence of immune dysfunction and subsequent chronic inflammation triggered by acute infection (del Rio et al. 2020, Greenhalgh et al. 2020).

To better understand the contribution of inflammation to the development of Long COVID symptoms, study participants will receive a series of questionnaires that address the most commonly reported symptoms that qualitatively and quantitatively evaluate the presence and nature of residual (post-Study Day 40) complaints of fatigue, malaise, affective symptoms, inflammatory cognitive dysfunction syndrome and associated functional limitations.

2.2 Nonclinical Studies of INB03

As mentioned in Section 2.1.2, the ideal therapy to treat ARDS in COVID-19 will quickly reduce inflammation in the lung without impairing the immune response needed to clear the virus. INB03 has been tested in multiple models of disease whose findings support its use to treat ARDS in COVID-19 patients. These studies are summarized below.

- In an animal model of allergic lung inflammation, INB03 reduced; i) the recruitment of inflammatory cells (lymphocytes and eosinophils), ii) levels of erythropoietin activity, iii)

inflammatory factors in the lung. INB03 suppressed ovalbumin (OVA)-induced airway hyperresponsiveness (Maillet *et al.* 2011).

- Multiple studies have shown that INB03 can reduce inflammation within hours of administration in rodents challenged with a variety of immunogens including; lipopolysaccharide (LPS), Group A Streptococcus (GAS) infection, and Bacillus Calmette-Guérin (BCG) infection. In a GAS model, INB03 reduced blood TNF protein levels at the earliest timepoint examined, 6 hours after treatment (Liu *et al.* 2019). Similarly, TNF, IL-6, and IFN γ were significantly reduced 8 hours after BCG-infected mice were challenged with LPS (Olleros *et al.* 2010). INB03 has also been shown to significantly reduce neuroinflammation following GAS infection within 48 hrs (Liu *et al.* 2019) and LPS challenge within 3 hours (*unpublished data*).
- INB03 is not immunosuppressive in animal models of infectious diseases. Immunosuppressive treatments including the currently available TNF and IL-6 antagonists increase risk of infection and ability to fight infections. For instance, in an animal models of BCG and Mycobacterium tuberculosis infection, inhibition of TNF by etanercept, which blocks both tmTNF and sTNF, increased pulmonary infiltrate and bacterial load which culminated in 100% mortality by day 30. By contrast, Mycobacterium tuberculosis-infected mice treated with INB03 had fewer pulmonary lesions, a reduced bacterial load, and normal survival (Olleros *et al.* 2009). Similarly, mice given a sublethal Listeria infection and treated with etanercept had a 100% mortality within a week. Not only did 100% of mice treated with INB03 survive, immunity was maintained (low bacterial load and liver microabscesses) (Zalevsky *et al.* 2007). Interestingly, INB03 significantly improved mortality in mice infected with Group A Streptococcus (median survival 11.5 days) compared to infected mice treated without INB03 (median survival 4 days) (Liu *et al.* 2019). In parasitic disease, INB03 did not affect parasitic load or survival in mice infected with trypanosome parasitemia (Vanwalleghem *et al.* 2017). Recently, and in collaboration with the National Institutes of Health (NIH), INB03 has been tested in mice infected with Eastern Equine Encephalitis and Coxsackie virus B to determine whether INB03 increased mortality in viral infections (*unpublished data*). In each case, there was no impact on disease burden and survival further demonstrating that INB03 provides potent anti-inflammatory effects without suppressing the immune system's ability to fight infection.

Please refer to the INB03 Investigator's Brochure (IB) for data on the nonclinical pharmacokinetic and toxicokinetic studies of INB03 conducted to date in rats and monkeys.

2.3 Clinical Studies of INB03

Please refer to the INB03 IB for data on clinical studies conducted to date.

2.4 Known and Potential Risks

This will be the first study of INB03 in patients with pulmonary complications of COVID-19. However, INB03 has been well tolerated in pivotal toxicology studies conducted in rats and

cynomolgus monkeys. Until there is more data from human trials, all risks are potential and are based on animal data and events that have been noted with other TNF-antagonists.

Currently, INB03 is being evaluated as a potential therapeutic protein with a planned once a week SC injection in humans. As with any injected therapeutic protein, there is the potential for an anti-drug immune response. As a consequence, antibodies which develop in response to drug treatment (immunogenicity) to native TNF or INB03 is a critical safety concern and will be closely monitored throughout the clinical studies.

Injection or allergic reactions may occur. Precautions for anaphylaxis will be observed during INB03 administration.

2.5 Dose Justification

INB03 is delivered as a subcutaneous dose once-a-week. For this trial, the first dose will be administered on Study Day 1 and a second dose on Study Day 8 if participant remains in hospital. The dose planned in this Phase 2 study is 1mg/kg once a week by SC injection. The dosing decision is based on the mechanism of action, the pharmacology in a non-human primate model and human data for the completed Phase I study in oncology (refer to the INB03 IB). To effectively neutralize 99.99% of sTNF in blood, trough blood levels of drug must be at 2 logs least 2 logs greater than the TNF level in blood. TNF levels in blood rarely exceed 100pg/ml (Diao *et al.* 2020). Thus, a trough level of more than 10,000pg/ml is adequate. This is the trough level obtained in the oncology Phase I trial using 1mg/kg/week SC dosing.

The drug has extensive pre-clinical pharmacokinetic and pharmacodynamic testing that is part of FDA IND# 100,130 that was opened for the treatment of Rheumatoid arthritis. No dose limiting toxicity (DLT) was determined in those studies. A no-observed-adverse-effect-level (NOAEL) was determined in a rodent model as 10mg/kg per day. The pathology noted on the NOAEL was vacuolated macrophages at the injection site. This was thought to be caused by the PEGylation. The proposed dose of 1mg/kg once a week is 70 times lower than the NOAEL dose. Furthermore, this dose has been used in more than 9 human participants with a single case of injection site inflammation. Otherwise the drug has been well tolerated for up to 117 days (14 weeks).

3 OBJECTIVES AND PURPOSE

3.1 Primary Objective

The primary objective of the study is to:

- Evaluate if INB03 given as a SC injection can decrease disease progression defined as death or requirement for mechanical ventilation in participants with pulmonary complications from COVID-19 infection.

3.2 Secondary Objectives

The secondary objectives of the study are to:

CONFIDENTIAL

- Assess the effect INB03 has on all-cause mortality in participants with pulmonary complications from COVID-19 infection;
- Determine if INB03 can decrease non-respiratory catastrophic complications of COVID-19 infection including admission to ICU, new onset neurologic, cardiovascular or thromboembolic disease, or renal failure;
- Evaluate if treatment with INB03 reduces increase in the WHO Ordinal Scale for Clinical Improvement score;
- Evaluate if length of hospital-stay in participants with pulmonary complications from COVID-19 decreases when treated with INB03;
- Evaluate the safety and tolerability of INB03 when given to participants with pulmonary complications from COVID-19 infection;
- Assess the effect INB03 has on inflammatory markers in participants with pulmonary complications from COVID-19 infection.

3.3 Exploratory Objectives

The exploratory objective of the study is to:

- Qualitatively and quantitatively evaluate the presence and nature of residual (post-Study Day 40) complaints of fatigue, malaise, affective symptoms, inflammatory cognitive dysfunction syndrome and associated functional limitations.

4 STUDY DESIGN AND ENDPOINTS

4.1 Description of the Study Design

The trial is a Phase 2, double-blind, placebo-controlled, randomized clinical trial of INB03 in participants with pulmonary complications from COVID-19 infection. Each participant will complete up to 6 study visits.

Screening: Participants with a diagnosis of COVID-19 will be screened for study eligibility. Prior to any trial related procedures, participants will provide their consent to participate in the clinical trial. Screening assessments will include:

- collection of medical history/participant demographic (including race and ethnicity);
- physical examination (including vital signs, height and weight);
- room air oxygen saturation (SaO₂), if possible;
- chest imaging;
- ECG;
- WHO Ordinal Scale for Clinical Improvement (to be completed any time after informed consent is obtained and up to 1-hour post-randomization on Day 1);
- clinical laboratory evaluations (as per [Table 2: Clinical Laboratory Evaluations](#));

CONFIDENTIAL

- serum or urine pregnancy test for women of childbearing potential (WCBP).

If any of the above assessments are performed as part of routine clinical care within 1 day of Screening, they do not need to be repeated.

Study Day 1: Eligible participants will be randomized to receive either INB03 at 1mg/kg by subcutaneous injection (SC) + standard of care (SOC) or Placebo SC injection + SOC within 1 day of Screening. Participants will receive their first dose of study drug after randomization. Blood samples to check TNF levels and perform an anti-drug antibody test will be collected before dosing. Clinical assessments while participants are inpatients will be as per routine management of hospitalized COVID-19 patients including daily collection of vital signs, physical exam, concomitant medications and laboratory evaluations. 12-lead ECGs and chest imaging assessments will be performed if deemed clinically necessary. Additionally, use of non-mechanical ventilation will be collected daily until the participant is discharged from hospital.

The WHO Ordinal Scale will also be completed daily until the participant is discharged from hospital.

The sponsor recognizes that SOC may change over time. The study protocol allows therapies that have shown benefit in well-designed prospective randomized trials. Each clinical site can select their SOC.

Study Day 8: Participants will be given a second dose of INB03 or Placebo on Day 8 (7 days after randomization) if they remain in hospital. Clinical assessments while participants are inpatients will continue as per routine management of hospitalized COVID-19 patients and described in [Table 3](#) – the Schedule of Assessments (SOA).

Since the timing of hospital discharge in this patient population cannot be predicted, discharge assessments will be obtained on the day the participant is to be discharged. If the participant remains in the hospital, the participant will continue with daily assessments as per [Table 3](#) - SOA. At discharge, no additional follow-up is expected until the participant is seen for the Study Day 28 visit.

Study Day 28: A follow-up visit will be conducted on Day 28. Follow-up study assessments will include:

- physical examination (including vital signs);
- room air oxygen saturation (SaO₂), if possible;
- chest imaging (if deemed clinically necessary);
- ECG;
- clinical laboratory evaluations (as per [Table 2: Clinical Laboratory Evaluations](#));
- adverse events;
- assessment of disease progression and use of non-mechanical ventilation;
- WHO Ordinal Scale for Clinical Improvement.

If participant is still in hospital at Study Day 28, no additional follow-up is expected until the participant is seen on the Day 40 final safety visit.

Study Day 40: A final visit will be conducted on Day 40. End of study safety assessments will be conducted as per [Table 3](#) - SOA.

Study Day 40-50: Participant will complete Long COVID questionnaires using an electronic Patient-Reported Outcomes (ePRO) portal. Assessments will include the Patient Health Questionnaire-9 (PHQ-9) and a Long COVID questionnaire (LCQ). The LCQ is a composite questionnaire that assesses Function and Performance, somatic and cognitive complaints reported to be associated with Long COVID syndrome. Additionally, the questionnaire captures life changes associated with COVID societal restrictions that existed or were anticipated prior to and *independent* of the participant's COVID-19 disease.

The Long COVID Informant questionnaire (LCIQ) will be completed by an informant, defined as someone who has known the participant for at least two years and interacts (face to face or via phone) for at least 4 hours per week beginning prior to contracting COVID-19, in person at the Study Day 40 visit or by phone. A separate informed consent form will be collected from the informant prior to completion of this questionnaire.

Study Day 50-70: In a subset of participants who report Long COVID symptoms, a telephone interview will be conducted by a third-party neuropsychologist to qualitatively and quantitatively evaluate the presence and nature of residual (post-Study Day 40) or emergent complaints of fatigue, malaise, affective symptoms, inflammatory cognitive dysfunction syndrome and associated functional limitations. This interview will consist of a semi-structured interview and open-ended questions to catalogue residual complaints which will be subjected to concept matching exercises to estimate the need for amending the LCQ to capture COVID-19 specific residuum. The interview time is estimated to be 45 minutes. Data captured during the semi-structured interviews will be de-identified and stored securely in electronic format.

Study Day 70: Participants will be contacted via telephone on Day 70 to assess AEs and changes in concomitant medications.

All laboratory, ECG, and vital signs data will be captured for data analysis and safety.

4.2 Study Endpoints

4.2.1 Primary Endpoint

The primary endpoint of the study is:

- Proportion of participants with disease progression from randomization to 28 days post-randomization, where disease progression is defined by the development of need for mechanical ventilation or death. Mechanical ventilation includes CPAP, BIPAP or mechanical ventilation requiring intubation.

4.2.2 Secondary Endpoints

The secondary endpoints of the study are:

- Proportion of participants with all-cause mortality;
- Proportion of participants who transfer to ICU level care by Day 28 (ICU level care is defined as a hospital setting where patient to nurse ratio is < 4);
- Proportion of participants with a new onset of neurologic disease (requiring medical intervention), including stroke by Day 28;
- Proportion of participants with evidence of new CHF or new MI requiring medical intervention by Day 28;
- Proportion of participants with a new onset embolus or thrombus by Day 28;
- Proportion of participants who develop a need for renal replacement therapy (defined as need for any type of dialysis including intermittent or continuous peritoneal or hemodialysis) by Day 28;
- Proportion of participants with an increase in the WHO Ordinal Scale of Clinical Improvement score at any time during the study;
- Length of hospital stay defined as the number of days in hospital from time of randomization to time of discharge or death, whichever occurs first;
- Change from baseline in inflammation markers over time.

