	
INB03 vs. Placebo. The primary endpoint treatment comparison will be evaluated using a one-sided $\alpha=0.005$ significance level. The odds ratio and corresponding 95% confidence intervals will be provided.
 
A supportive analysis will be performed using logistic regression with treatment and covariates of age and co-morbidities at baseline included in the model. Additional covariates may be added to the model and defined in the SAP.
 
Sensitivity and supplementary analyses will also be performed and are described in the protocol.
 
Binary secondary endpoints will be analyzed similarly to the primary endpoint using a CMH test, and continuous secondary endpoints, such as length of hospital-stay and change from baseline in inflammatory markers, will be analyzed using an analysis of covariance (ANCOVA) model and will include treatment and covariates such as age and number of co-morbidities.
 
Exploratory endpoints will be summarized by treatment group and may be analyzed similarly as the primary and secondary endpoints. Analysis of interview data collected on a subset of participants will be summarized in a separate report.
 
Interim Analysis:
 
An interim analysis will be performed when approximately 70 participants who meet the mITT population definition and have completed the Study Day 28 visit or who had an intercurrent event prior to Day 28. In order to maintain study blind, an independent unblinded statistical team will perform the analyses and present the results to the data monitoring committee (DMC).
 
The primary efficacy endpoint will be analyzed and a limited number of individuals who are not involved in the study conduct or review of day-to-day activities of the study will be informed on the unblinded efficacy results in order to plan further development and inform on other corporate objectives.
 
The DMC will also review unblinded safety and the primary efficacy data and recommend to the sponsor their unbiased opinion concerning safety and efficacy of INB03 in an acute COVID population.
 
Safety Analysis:
 
Safety data including AEs, vital sign measurements, ECGs, clinical laboratory information, and concomitant medications will be summarized descriptively for the safety population by treatment arm and overall. The safety set is defined as all randomized participants who have received any amount of study drug. AEs will be coded using the Medical Dictionary for Regulated Activities (MedDRA) classification system and summarized by System Organ Class and Preferred Term. For parameters measured over time, absolute values and changes from baseline will be summarized for each time point.

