9.5.2 Secondary Endpoints

Descriptive statistics will be provided for each secondary endpoint and reported by treatment group. Absolute values and changes in inflammatory markers as well as the WHO Ordinal Scale for Clinical Improvement collected each day in hospital will be presented by day and treatment group. Length of stay in index hospital will also be descriptively summarized. The number and percent of participants with the following will be summarized by treatment group:

- Have a 1 point, 2 point etc. increase/decrease in WHO Ordinal Scale
- All-cause mortality at any time within Day 28 visit
- Transfer to ICU level care within Day 28 visit
- Have a new onset of neurological disease within Day 28 visit
- Have evidence of new CHF or new MI requiring medical intervention within Day 28 visit
- Have new onset of embolus or thrombus within Day 28 visit
- Develop need for renal replacement therapy within Day 28 visit

Graphical presentation of endpoint data may be presented and will be described in the SAP.

The secondary estimand population for all secondary endpoints will be estimated based on the mITT population and includes randomized participants who have been diagnosed with COVID-19, have at least one co-morbidity, are admitted to the hospital and have pulmonary complications due to COVID-19 who receive any amount of study drug. To estimate this estimand, all post-randomization data up until Day 28 of the study will be used in the evaluation of each secondary endpoint. Specific handling of intercurrent events for each secondary estimand will be defined in the SAP.

The statistical analyses for secondary estimators with binary outcomes will be performed using CMH tests similar to the primary estimator. In addition, logistic regression analyses as described for the primary efficacy estimator may be performed. Treatment arm will be included in the model as well as age and number of co-morbidities at baseline as covariates. Parameter estimates, odds ratio and the corresponding 2-sided 95% CIs will be provided.

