6.2.2.1 Continuous Endpoints

Descriptive statistics will be provided for each endpoint and will be reported by treatment arm. Endpoints that are not normally distributed will also display geometric means. Absolute values and changes from baseline will be presented for the following:

- Inflammation markers (COVID-19 Specific markers: eGRF, Troponin, CRP, Ferritin, D-dimer)
- WHO Ordinal Scale for Clinical Improvement

Baseline will be defined as the value in the database prior to receiving any amount of study treatment. Line plots of means with error bars for the above endpoints will be presented by treatment group. Figures of means for both absolute values at each timepoint and the changes from baseline will be provided.

Changes from baseline will further be analyzed statistically using a mixed model repeated measures (MMRM) analysis. Factors include treatment arm, timepoint, age (≤ 50 , >50 to 65 , >65) and number of co-morbidities (1, 2, 3+). The baseline value of the endpoint will be included as the covariate. Patient will be repeated by timepoint. An unstructured covariance and the Kenward Roger's approximation for the degrees of freedom will be assumed. Least-square means will be provided for the treatment differences (INB03 + SofC vs Placebo + SofC) as well as the corresponding 95% CIs.

Descriptive statistics will be provided for the following endpoints and reported by treatment arm.

- Length of stay in index hospital
- Days to disease progression

Length of stay in index hospital will be derived as the index hospital discharge date – randomization date +1. Time will be considered in the derivation if collected for both dates. If discharge date is missing, date of death or end of study date will be used, whichever comes first.

Days to disease progression is not a specified secondary endpoint in the clinical study protocol, however is of interest to summarize. Days to disease progression will be derived as the first date of disease progression – randomization date +1. Intercurrent events, as defined in Section 6.2.1.3, will be considered when assigning a patient as having disease progression. Patients with no disease progression and who have completed the study will be censored as the duration on study. Patients who terminated the study early and with no disease progression according to Section 6.2.1.3 will be censored and given the longest duration, 40 days.

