A multi-factor analysis of variance (ANOVA) will be used to assess the differences between treatment arms for each endpoint. Treatment arm, age (≤ 50 , >50 to 65 , >65) and number of co-morbidities (1, 2, 3+) will be included as factors in the model. Least-square means will be provided for the treatment differences (INB03 + SofC vs Placebo + SofC) as well as the corresponding 95% CIs. If assumptions for ANOVA are not met then a comparable non-parametric test will be performed (e.g., rank ANOVA or Wilcoxon rank-sum tests).

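### Length of hospital stay counts death as if it were discharge, so the comparison can favour the arm with more early deaths; the SAP should rank death worst for this test

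*Protocol*

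**What the plan says.** The secondary objective in Protocol 3.2 treats a shorter stay as benefit: "Evaluate if length of hospital-stay in participants with pulmonary complications from COVID-19 decreases when treated with INB03". Protocol 4.2.2 gives the endpoint as "Length of hospital stay defined as the number of days in hospital from time of randomization to time of discharge or death, whichever occurs first", and the objectives table in SAP 2 repeats that definition.

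SAP 6.2.2.1 turns it into a variable: "Length of stay in index hospital will be derived as the index hospital discharge date – randomization date +1". For participants without a discharge date it adds: "If discharge date is missing, date of death or end of study date will be used, whichever comes first".

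The comparison follows in the same section: "A multi-factor analysis of variance (ANOVA) will be used to assess the differences between treatment arms for each endpoint". The factors are treatment, age group and number of co-morbidities. If the model assumptions fail, "a comparable non-parametric test will be performed (e.g., rank ANOVA or Wilcoxon rank-sum tests"). The protocol synopsis names ANCOVA for this endpoint; that difference does not matter here, because both models work on the same days.

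Protocol 9.5.2 promises that "Specific handling of intercurrent events for each secondary estimand will be defined in the SAP". SAP 6.2.2.2 does so for the binary secondary endpoints (treatment policy), and SAP 6.2.2.1 refers days to progression back to the primary rules. For length of stay the SAP names no strategy. The only rule is the date substitution above.

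**The concern.** A stay can end because the participant recovered or because the participant died. The variable does not distinguish the two, so the worst outcome in the trial can receive one of the best values. The least-squares mean difference and its confidence interval then mix the drug's effect on recovery with its effect on the frequency and timing of death. The rank fallback does not help, since an early death keeps a low, favourable rank.

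The end-of-study fallback has a similar effect: an inpatient who withdraws or is lost on Day 4 scores a four-day stay.

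At stake is the reading of one secondary result. A drug that brought deaths forward could appear to shorten hospitalisation, and a drug that prevented early deaths could appear to lengthen it.

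**Working it through.** **Inputs.** The plan gives no mean stay, standard deviation, mortality rate or time of death, so there is no figure to reproduce. Values of m, L and D below are assumptions. The numbers per arm come from the documents: 173 planned (Protocol 9.1, SAP 3.3), and 77 dosed (SAP 6.2.4), about 38 per arm.

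**Step 1: how one participant scores.** Stay = end date - randomization date + 1, with randomization on Study Day 1.
- Discharged alive on Day 9: 9 - 1 + 1 = 9 days.
- Died in hospital on Day 3: 3 - 1 + 1 = 3 days.
- Withdrew as an inpatient on Day 4: 4 - 1 + 1 = 4 days.

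**Step 2: arm means.** Let m be in-hospital mortality, L the mean stay of survivors and D the mean day of death.

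Mean stay = (1 - m)L + mD

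If L and D are the same in both arms, INB03 minus placebo = (mT - mP)(D - L). With more deaths on INB03 this is negative (apparent benefit) when D < L, zero when D = L and positive when D > L.

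**Step 3: illustration.** L = 9, mP = 10%, mT = 20%.

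| How deaths are scored | Placebo | INB03 | Difference |
|---|---|---|---|
| Day 5, as planned | 0.9×9 + 0.1×5 = 8.6 | 0.8×9 + 0.2×5 = 8.2 | -0.4 |
| Day 9, as planned | 9.0 | 9.0 | 0.0 |
| Day 12, as planned | 0.9×9 + 0.1×12 = 9.3 | 0.8×9 + 0.2×12 = 9.6 | +0.3 |
| Every death scored 28 | 0.9×9 + 0.1×28 = 10.9 | 0.8×9 + 0.2×28 = 12.8 | +1.9 |

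With the arms exchanged, so that INB03 halves mortality, deaths at Day 5 make it look 0.4 day worse. Deaths at Day 12 make it look 0.3 day better, which is the right direction but well short of the 1.9 days obtained when death is scored at 28.

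**Step 4: range.** Take mortality of 5% vs 10%, 5% vs 15% or 10% vs 20%, with L from 8 to 16 and D from 3 to 5. The planned difference runs from 0.05×(5 - 8) = -0.15 to 0.10×(3 - 16) = -1.30 days. With L = 8 and D = 12 it is +0.2 to +0.4. Timing alone is enough: at 10% mortality in both arms, moving deaths from Day 10 to Day 4 on one arm gives 0.10×(4 - 10) = -0.6 day.

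**Step 5: simulation.** There were 4,000 trials per scenario. Survivor stay had mean 12 and SD 6 days in both arms. A plain t-test on the stay as defined stands in for the planned ANOVA; the alternative is a Mann-Whitney test with deaths ranked worst. The two-sided p<0.05 is only a marker, since SAP 5.1 sets a default two-sided 1% level.

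| Per arm | Mortality, placebo vs INB03 | Mean death day, placebo vs INB03 | Estimate favours INB03 | p<0.05 for INB03, as planned | p<0.05 for / against INB03, deaths worst |
|---|---|---|---|---|---|
| 173 | 5% vs 10% | 6 vs 6 | 68% | 6.8% | 0.2% / 12.8% |
| 173 | 10% vs 20% | 6 vs 4 | 93% | 31.9% | 0.0% / 36.5% |
| 38 | 10% vs 20% | 6 vs 4 | 76% | 10.6% | 0.2% / 11.8% |

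The second and third rows combine doubled mortality with earlier death on INB03, so they are deliberately unfavourable cases.

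**The case against.** The definition can be defended as a measure of bed use. Protocol 2.1.2 gives relief of pressure on the health system as a goal, and days occupied until discharge or death is a legitimate resource quantity. All-cause mortality is a separate secondary endpoint compared by a CMH test, so a reader sees deaths beside the stay. Secondary p-values are nominal and carry no formal claim (Protocol 9.5, SAP 6.2.5).

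This limits the consequence but does not remove it. A separate mortality row does not correct the stay difference or its interval, and the stated objective concerns benefit to participants, not bed use.

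Three stronger readings are tempting, and the documents support none of them.
- A reader might infer that death is expected to differ by arm because it is part of the primary endpoint. The only planning figures, 21% and 7%, are for the composite, which also counts CPAP, BIPAP and intubation. It could differ through ventilation alone, and the rationale hopes only for fewer deaths on INB03.
- A reader might infer that the comparison always works against a life-saving drug. It does so only when the deaths precede the typical discharge day.
- A reader might infer that days alive and out of hospital can be derived from dates already collected. The SAP variable covers the index hospital, no follow-up is expected between discharge and Day 28 (Protocol 4.1), and the documents do not show that readmission dates are captured.

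It also stands that changing a tested quantity after enrolment has closed, with an unblinded look at primary efficacy planned before final lock (SAP 6.2.4), needs more care than a wording edit.

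**Conclusion.** The concern holds in a conditional form. As defined and derived, length of stay treats death like discharge, and neither ANOVA nor the rank fallback corrects for it. If mortality differs between arms and deaths come before the usual discharge day, the comparison favours the arm with more early deaths. If deaths come later, the sign is right but the difference is attenuated. Which case applies cannot be told from the documents.

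The sizes in the working rest on assumed mortality, survivor stay and death timing, with survivors' stay equal in the two arms. They show what the definition can do; they do not predict this trial's result. The documents give no ground for inferring that INB03 raises mortality or that the reported stay will have the wrong sign. The effect is confined to a nominal secondary endpoint. It deserves correction because the protocol promised a rule for intercurrent events on this endpoint and the SAP does not name one.

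**What to change.** Amend SAP 6.2.2.1 before final unblinding. Staff blinded to the preliminary efficacy results should make the change, and it should be recorded in SAP 1.1.

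- **Tested quantity.** Index-hospital stay to Day 28, ranked. Death by Day 28 takes the worst rank, including death after discharge; still in hospital at Day 28 is next worst; the rest are ranked by day of discharge.
- **Test.** A stratified rank (van Elteren) test on the primary strata. These form 3 × 3 = 9 cells for 77 dosed participants, so apply the collapsing rule in SAP 6.2.1.2.
- **Leaving the study as an inpatient without a discharge date.** Do not let the end-of-study date create a short stay. Treat loss to follow-up as unfavourable, as SAP 6.2.1.3 does for the primary endpoint. For withdrawals, state the rank used and vary it in a sensitivity analysis.
- **Reporting.** Keep the protocol-defined length of stay as a descriptive table split by discharged alive and died.
- **Days alive and out of hospital.** Use this only if readmission dates are confirmed to be in the database.

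The cost is one derived variable, a SAP amendment and a tested scale less familiar than mean days. The familiar figure stays in the tables.
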